4.1. Fixation and inclusion

Samples were taken at six months after regeneration and were treated with non-demineralized histology. At the time of sampling, the samples were fixed in LILLIE neutral formolin, diluted to 10% in buffered sodium phosphate pH 7.4. The fixation period lasted 3 weeks. The samples were then rinsed under running water for 48 hours.

The dehydration of the samples was carried out in alcohol baths of increasing concentration and for 48 hours in each bath, in ethanol 70°, 80°, 90°, 95°, 100°, 100°, then the clarification, allowing the penetration of methacrylate, in 2 successive xylene baths of 24 hours each.

4.2. Cutting technique

The blocks were cut under irrigation and at slow speed with an Exact saw (Cutting machine EXACT-APPARATEBAU Nordersted, Germany), so as to take cuts of at least 80 μm . These cuts were subsequently reduced in thickness with the Exact abrasion system. The polishing was carried out with abrasive paper discs of decreasing granulometry making it possible to reduce the thickness of the cuts automatically to the desired value. The cuts were separated into S (superficial), M (median) and P (profound) cuts, the superficial ones being the cuts facing the periosteum.

4.3. Staining

The sections were stained with Giemsa-Paragon and basic fushin.

Giemsa will give cells and nuclei the colour blue, and Paragon will stain bone in red.

5. Histomorphometry

The qualitative observation of the sections was done under a digital microscope (Keyence digital microscope VHX-6000) with normal and polarised light visualisations. For histological quantification, an optical microscope was used (Olympus BX 60, Olympus Corporation, Tokyo, Japan) connected to a digital camera (Olympus E330), along with the software Image J/ Fiji.

It was first calibrated by measuring the scale bar present on the image. The image was made into black and white (Type: 8-bit). The scale was set by measuring the length of the scale bar in pixels and by setting its known distance in millimetres. It was then set as 'Global' for all the images with the same scale.

The total area of the concerned section was measured. Then the bone and osteoid volume were quantified using the Bone Volume Mask and by using the 'wand tool' to select all the black areas. The percentage of bone and osteoid matrix in each section was consequently calculated.

**A clinical, radiographic and histological prospective study**

Statistical Analysis Plan

Date: March 8, 2019

The statistical package software for social sciences (SPSS for Windows, Chicago, IL, USA, version 25.0) was performed for statistical analysis of the data. The alpha error was set at -p-value<0.05. Frequency and percentage were utilized to describe categorical variables. Mean and standard-deviation were used for continuous variables.

- Repeated measure analysis of variance with two within-subjects factors (Time: Baseline and six months; distance: 0mm, 2mm, 4mm, and 6 mm) was performed to compare the mean bone level within groups. It was followed by univariate analyses and Bonferroni post hoc tests.
- Repeated measure analysis of variance with one within-subjects factor (distance: 0mm, 2mm, 4mm, and 6 mm) followed by Bonferroni post hoc tests was used to compare the mean horizontal gain.
- Repeated measure analysis of variance with one within-subjects factor (level: buccal, median, lingual) followed by Bonferroni post hoc tests was executed to compare the mean vertical gain.
- One sample t tests were used to compare the mean vertical gain with a theoretical value “0” that supposed the absence of gain.
- Student t tests were performed to compare continuous variables between two groups.
- Pearson correlation coefficients were calculated to assess the relationship between continuous variables.

Kruskal-Wallis tests were used to compare histomorphometric measurements between different levels.

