1.3. Fixation

The fixation system used was the Pro-fix™ Precision Fixation System, consisting of self-drilling membrane fixation screws of 1.5 mm x 3.0 mm.

2. Study design

Fourteen patients (1 male, 13 females) aged between 27 and 64 years old were selected from the Department of Periodontology of the Faculty of Dentistry, XXXXXX

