3.4.1. Horizontal bone width measurements

For each implant site, pre and post-operative horizontal bone width were measured at 4 levels. Bone width was calculated from the distance between the most buccal and most lingual bone points at each level while being parallel to the simulated implant platform.

- H0-T1 and H0-T2: Pre and post-operative horizontal bone width at implant platform level.
- H2-T1 and H2-T2: Pre and post-operative horizontal bone width at 2mm apically to implant platform.
- H4-T1 and H4-T2: Pre and post-operative horizontal bone width at 4mm apically to implant platform.

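### Optional, low-severity improvement: Holm's step-down could replace the (valid) Bonferroni post hoc tests in SAP bullets 1 to 3 at the same 5% familywise bound, for a usually modest gain in power

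*SAP*

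**What the plan says.** The SAP sets the significance level once: "The alpha error was set at -p-value<0.05". Sidedness is not stated. Its first three bullets are repeated-measures ANOVAs, and all three name Bonferroni for the follow-up comparisons:

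- Bullet 1, bone level by time (two points) and distance (0, 2, 4 and 6 mm): "It was followed by univariate analyses and Bonferroni post hoc tests".
- Bullet 2, horizontal gain over the four distances: "followed by Bonferroni post hoc tests was used to compare the mean horizontal gain".
- Bullet 3, vertical gain over three positions: "level: buccal, median, lingual) followed by Bonferroni post hoc tests was executed to compare the mean vertical gain".

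No step-down or other multiplicity method is mentioned. For bullet 1 the SAP does not say which comparisons form the family.

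Section 2 of the Protocol gives the sample: "Fourteen patients (1 male, 13 females) aged between 27 and 64 years old were selected". Section 3.4.1 makes the implant site the unit of measurement: "For each implant site, pre and post-operative horizontal bone width were measured at 4 levels". The number of sites is not given. Neither document contains a power calculation, effect size, SD or within-patient correlation.

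**The concern.** Bonferroni holds every pair to the strictest threshold, even after other pairs have been rejected. With four distances each of six pairs must reach 0.0083; with three vertical levels each of three pairs must reach 0.0167. Holm relaxes the threshold as rejections accumulate and keeps the same familywise bound. If the reader wants to know at which depth or position the gain differs, Bonferroni leaves some power unused. A pair that misses the threshold may then be read as showing no difference. Only comparisons between levels are at stake.

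**Working it through.** **Inputs.** Alpha 0.05 (SAP; two-sided assumed). Four distances and three vertical levels (SAP bullets 1 to 3). n = 14 (Protocol section 2). SD, correlation and mean pattern are assumed, because the documents give none. There is no planned power figure to reproduce.

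**Step 1, size of each family.** m = k(k − 1)/2. Four distances: 4 × 3/2 = 6. Three levels: 3 × 2/2 = 3.

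**Step 2, thresholds.** Bonferroni uses α/m for every pair; Holm uses α/(m − i + 1) for the i-th smallest p-value.

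| Family | Bonferroni | Holm, in order |
|---|---|---|
| 6 pairs | 0.0083 | 0.0083, 0.0100, 0.0125, 0.0167, 0.0250, 0.0500 |
| 3 pairs | 0.0167 | 0.0167, 0.0250, 0.0500 |

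With 13 degrees of freedom, the critical |t| stays at 3.107 for all six pairs under Bonferroni. Under Holm it falls from 3.107 to 2.160.

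**Step 3, dominance.** Every Holm threshold is at least α/m. If a p-value is at or below α/m, so are all smaller ones, and Holm reaches and rejects it.

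**Step 4, error control.** Suppose m₀ nulls are true. The first true null that Holm could reject is met at step m − m₀ + 1 at the latest, so its threshold is at most α/m₀. The Bonferroni inequality over the m₀ true nulls then bounds the familywise error by α. Independence is not needed, so correlated levels on one ridge are no obstacle.

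**Step 5, familywise error in numbers.** Under independence with all nulls true, Bonferroni gives 1 − (1 − 0.05/6)^6 = 0.0490 and 1 − (1 − 0.05/3)^3 = 0.0492. In simulation (20,000 datasets per setting, n = 14, paired t tests) with all nulls true, both methods gave 4.3% for four levels and 4.3% for three. With some true nulls, Bonferroni against Holm gave:

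- 2.6% against 4.0% (four levels, one shifted by 1 SD, correlation 0.5);
- 1.7% against 3.5% (three levels, one shifted by 0.8 SD, correlation 0.5);
- 1.7% against 4.9% (three levels, one shifted by 1 SD, correlation 0.8), the highest Holm value seen.

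**Step 6, power at n = 14.** SD 1. CS means equal correlation between all levels; AR means correlation that decays with distance between levels.

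| Pattern | Correlation | Mean power per pair, Bonferroni → Holm | All true differences found |
|---|---|---|---|
| 4 levels, 0.25 SD steps | CS 0.5 | 14.0% → 15.3% | 0% → 0% |
| 4 levels, 0.25 SD steps | AR 0.8 | 19% → 23% | – |
| 4 levels, one 0.8 SD away | AR 0.5 | 35% → 37% | – |
| 4 levels, one 0.8 SD away | AR 0.8 | 69% → 73% | – |
| 4 levels, one 1 SD away | CS 0.5 | 72.6% → 76.4% | 48.5% → 57.2% |
| 4 levels, 0.5 SD steps | CS 0.5 | 48.3% → 54.9% | 0% → 1.2% |
| 4 levels, 0.5 SD steps | AR 0.8 | 69% → 83% | 9% → 44% |
| 3 levels, one 0.8 SD away | CS 0.5 | 60.3% → 64.5% | 43.2% → 51.6% |
| 3 levels, 0.5 SD steps | CS 0.5 | 43.0% → 48.3% | 2.4% → 9.1% |
| 3 levels, 0.5 SD steps | AR 0.8 | 71% → 81% | 35% → 60% |
| 3 levels, 0.8 SD steps | CS 0.5 | 73.7% → 84.1% | 31.8% → 58.5% |

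The large gains share one feature. The SD of a paired difference is √(2(1 − ρ)). Adjacent levels are therefore 0.5/√0.4 = 0.79 of that SD apart in the AR 0.8 step rows, and 0.8/√1 = 0.80 apart in the last row, and every pair truly differs. The chance of at least one correct rejection was essentially the same for both methods, for example 92.6% for both with four levels and one 1 SD away. In no simulated dataset did Bonferroni reject a pair that Holm kept.

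**Step 7, other sample sizes.** For four levels, 0.5 SD steps and CS 0.5, mean pair power rose by 54.9 − 48.3 = 6.6 points at n = 14, 69.8 − 61.2 = 8.6 at n = 20, and 82.0 − 71.4 = 10.6 at n = 28.

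**The case against.** The strongest reply is that nothing here is wrong. Bonferroni after a repeated-measures ANOVA is valid, and the SAP neither contradicts itself nor omits anything on this point. That stands: the change is optional.

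It can also be said that Bonferroni's conservatism buys something. That stands too. The nominal bound is the same, but when some nulls are true Bonferroni's actual familywise error is lower (step 5). It also gives matching simultaneous intervals directly. A reader might infer that Bonferroni offers no additional protection at all; the figures do not support that.

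Third, the SAP is written in the past tense, and Protocol sections 2.4 and 2.5 already report healing and the six-month scans. Moving now to a rule that rejects at least as often could look data-driven. This does not defeat the point, but it governs how the change is reported.

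Finally, no passage that can be read states the ranking of depths or positions as an objective, so the importance of these comparisons is inferred from the bullets.

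None of this touches the core result: on the same p-values and with the same nominal bound, Holm never rejects less.

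**Conclusion.** The point holds as a cheap improvement of low severity. The dominance of Holm over Bonferroni is a mathematical fact. The size of the benefit is not, because it rests on an assumed SD, correlation and mean pattern. At n = 14 the gain in mean power per pair is about 1 to 7 points in most settings. It reaches 10 to 14 points only where all levels are well separated: 0.5 SD steps with correlation 0.8, or the nearly equivalent 0.8 SD steps with correlation 0.5.

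Two stronger readings are tempting. One takes the rise from 69% to 83%, or from 9% to 44% for all six pairs, as the expected benefit. Nothing in the documents supports that scenario over the others, and with 0.5 SD steps at AR correlation 0.5 the all-six figure goes only from 0.1% to 2.6%. The other treats this as a small-sample problem peculiar to 14 patients. The argument holds at any n, the gain was larger at 20 and 28 in one pattern, and the analysed n may be implant sites, whose number is not given.

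Holm leaves the chance of at least one finding unchanged. It also leaves untouched the overall before/after comparison, which has two time points, and the one-sample t tests of vertical gain, which carry no stated adjustment.

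**What to change.** In bullets 2 and 3, replace the Bonferroni wording with *paired comparisons with Holm step-down adjustment (familywise alpha 0.05)*, over the 6 distance pairs and the 3 vertical-level pairs respectively.

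In bullet 1, define the follow-up families and apply Holm within each: the four baseline-to-six-month contrasts, one per distance (thresholds 0.05/4 = 0.0125, then 0.0167, 0.0250, 0.0500), and the 6 distance pairs at each time point.

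Keep Bonferroni simultaneous intervals beside the estimates. If the analysis has already been run, show the Holm results next to the Bonferroni results and label them as a change.

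Cost: a change of SAP wording and a short hand calculation on the unadjusted paired p-values. Holm has no equally simple simultaneous intervals, and it uses somewhat more of the allowed 5% error when some nulls are true.

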2.1. Inclusion criteria

Confining with the inclusion criteria, all the selected patients were systematically healthy, had good oral hygiene (FMPS and FMBS <20%). When presenting for implant placement and upon examination, the ridges had deficiencies in width (<4 mm, Cawood and Howell class IV) which did not allow correct implant placement. Therefore, horizontal bone augmentation procedures were proposed. All areas needing GBR, maxilla or mandible, posteriorly or anteriorly were included in this study.

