Sutures were removed at 14 days, they were left for another 7 days when found necessary to secure the healing.

Patients were told not to wear their prosthesis when present for a month at least, after that the prostheses were relined with a soft liner and were worn only occasionally.

Healing was uneventful in all cases except two where an exposure occurred along with suppuration. They were treated with an extended dose of Amoxicillin (2 weeks) and with chlorhexidine rinsing. In both cases the membrane was not removed and re-epithelialization occurred after seven to ten days.

2.5. *Implant placement*

[figure not shown]
At 6 months from the surgery, a CBCT scan of the grafted area was taken and measures were made for the choice of the implant diameter and length. In all of the post-operative CBCTs, implant placement seemed possible.

On the day of the implant placement, local anaesthesia was made, followed by a mid-crestal incision and occasionally a vertical one, allowing access to the fixation screws for their removal.

The crest was debrided from any soft tissue remnants and a biopsy was taken at the site of implant placement using a trephine burr of outer diameter of 3.5mm and inner diameter of 2.5mm (Meisinger®). The trephine and bone were immersed in 10% buffered formaldehyde and fixated for histology. The implants (Straumann®, Bone Level Cylindrical) were placed at the corresponding sites of the biopsies, and the choice of a cover or a healing screw was made depending on the clinical situation and the primary stability of the implant. In most of the cases, a 2 mm of bone structure was established buccally while positioning the implant.

Implant insertion torques were noted as indicated on the implant torque wrench.

Periapical radiographs were taken, the flap was sutured and the patients received a daily dose of 2g of Amoxicillin for 7 days and diclofenac potassium (Cataflam® 50mg) inflammatory for pain management. They were also notified to mouth rinse with Chlorhexidine 0.12% for 10 days.

a

b

Figure 6: View of the crest after biopsy (a) and implant placement in the mandible (b).

3. Radiological protocol

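### Kruskal-Wallis is named for histomorphometric levels that are undefined and, on the natural reading, matched within biopsy; a matched rank test is needed

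*SAP*

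**What the plan says.** The SAP closes with one sentence on histology: "Kruskal-Wallis tests were used to compare histomorphometric measurements between different levels". It does not say what the levels are, what the unit of analysis is, or how many values each patient contributes.

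The Protocol, section 4.2, describes the only division of the histological material: "The cuts were separated into S (superficial), M (median) and P (profound) cuts". These are sections of the samples described in section 2.5, where "a biopsy was taken at the site of implant placement using a trephine burr", and the implants "were placed at the corresponding sites of the biopsies". Section 5 gives the measurement: "The percentage of bone and osteoid matrix in each section was consequently calculated".

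Elsewhere the word level refers to radiographic positions. Protocol 3.4.1 says: "For each implant site, pre and post-operative horizontal bone width were measured at 4 levels". For vertical gain the SAP specifies "Repeated measure analysis of variance with one within-subjects factor (level: buccal, median, lingual", and it also treats distance (0, 2, 4 and 6 mm) as a within-subjects factor.

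**The concern.** Kruskal-Wallis compares groups made up of different, independent units. If the levels are the three cutting depths, each biopsy contributes to all three groups and the values are matched. The test then leaves between-biopsy variation in its error term, although that variation cancels when depths are compared within a biopsy. The SAP allows for such matching in its radiographic analyses but not here, and gives no reason. A wish for a rank method would not explain it, because Friedman's test is the matched rank test.

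At stake is whether the p-value for a depth difference in bone and osteoid percentage means what it appears to mean. The main danger is that a real gradient from the periosteal side inwards is reported as absent.

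**Working it through.** **Inputs from the documents.** 14 patients (Protocol 2); three depths (Protocol 4.2); alpha 0.05 (SAP). The plan gives no power, effect size or SD for this comparison, so there is no stated figure to reproduce.

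**Assumptions, not in the documents.** Normal data with total variance 1; the same correlation ρ between any two depths of a core; one complete set of three depths per patient; depth means shifted by 0, 0.4 and 0.8 SD for power.

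**Direction of the error.** The variance of a difference between two depth means is 2(1 − ρ)/n when values are matched. An independent-groups test in effect uses 2/n. With n = 14 and ρ = 0.5, that is 2 × 0.5/14 = 0.071 against 2/14 = 0.143. The test works with twice the true variance, so it rejects too rarely.

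**Size, by simulation** (40,000 runs per cell, n = 14; KW = Kruskal-Wallis, RM = repeated-measures ANOVA with Greenhouse-Geisser correction):

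| ρ | KW type I error | Power KW | Power Friedman | Power RM |
|---|---|---|---|---|
| 0 | 4.9% | 40% | 31% | 38.5% |
| 0.2 | 2.5% | 37% | 38% | 47% |
| 0.3 | 1.6% | 36% | 43% | 53% |
| 0.5 | 0.6% | 33% | 57% | 69% |
| 0.7 | 0.1% | 30% | 80% | 90% |

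Friedman's type I error is 4.8–5.0% and that of corrected RM 4.3–4.5% throughout. Independent repeats put the KW figure at ρ = 0.5 between 0.5 and 0.7%.

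**When the error could exceed 5%.** Suppose each patient gives c cores and each core k cuts per depth, all entered as separate values. Write P for patient, PD for patient-by-depth, C for core and CD for core-by-depth variance; the rest is residual E.

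- True variance of a difference between depth means: (2/n)[PD + CD/c + E/(ck)].
- Variance the test works with: (2/n)(P + PD + C + CD + E)/(ck).
- Multiplying both by nck/2 and subtracting, the first is the larger when (ck − 1)PD + (k − 1)CD > P + C.

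Examples with 14 patients and no true depth effect:

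- P/PD/C = 0.1/0.3/0.1, k = 1, P + C = 0.2. Two cores: 1 × 0.3 = 0.3 > 0.2, simulated error 6.7%. Three cores: 2 × 0.3 = 0.6 > 0.2, 11.6%.
- P/PD/C = 0.3/0.2/0.2, k = 1, P + C = 0.5. Two cores: 0.2 < 0.5, 2.0%. Three cores: 0.4 < 0.5, 4.2%.
- One core, three cuts per depth, C = 0.5, CD = 0.3: 2 × 0.3 = 0.6 > 0.5, 8.6%.

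Inflation is therefore possible but not the general rule: 8 of 14 multi-core settings and 27 of 42 multi-cut settings tried lay below the boundary.

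**The case against.** **The premise is inferred.** The Protocol calls the depths cuts, not levels, and does not say that every core yielded all three. This stands. The firm fault is an undefined factor and unit; that the test is wrong follows only on the depth reading. No competing histological division appears in the documents, however, and nothing says the three depths came from different patients.

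**The size is assumed.** No correlation or variance component is documented. At zero correlation Kruskal-Wallis is close to nominal and has more power than Friedman's test (40 against 31%). This also stands, and is why a range is shown.

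**A reader might infer that significant results are unreliable too.** Eligibility was broad ("All areas needing GBR, maxilla or mandible, posteriorly or anteriorly were included in this study"), biopsies and cuts appear in the plural, and percentages are per section, so several values per patient and depth are conceivable. But the eligibility statement concerns areas, not cores per patient, and the plurals fit 14 patients with one core each. The documents show neither several cores per patient nor separate entry of cuts, and inflation would also need depth-specific variance beyond the boundary above. In the simple case the error rate is 0.1–4.9%, so a significant result stands.

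**A reader might infer that repeated-measures ANOVA should be the main test,** since the SAP uses it elsewhere and it has the highest power at the positive correlations tabulated. That rests on normal data, which the documents do not establish, and the SAP chose a rank test here. With lognormal data at log-SD 1 and correlation 0.5, corrected repeated measures has 33.5% power, Kruskal-Wallis 32.7% and Friedman 56.5%. Such skew is not established either, but Friedman's test is the like-for-like repair.

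**Conclusion.** The point holds conditionally and is worth fixing; confidence is medium because the depth reading is inferred. On that reading, with one core per patient, one value per depth and positive within-core correlation, the planned test is conservative. At correlation 0.5 it gives up about 24 percentage points of power to Friedman's test (57 − 33) for the assumed shift. A non-significant depth comparison would then be weak evidence of no difference. Friedman's advantage disappears below a correlation of about 0.2.

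The documents do not support a claim of inflated false positives; that question stays open until the numbers of cores and cuts are reported. The radiographic analyses and the descriptive bone percentages are unaffected, and no document names this comparison as primary.

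**What to change.** 1. Define the histomorphometric levels and the unit of analysis in the SAP.
2. If the levels are the three depths, average cuts within core and depth, then cores within patient, to one value per patient and depth.
3. Replace Kruskal-Wallis with Friedman's test as the main test, followed by Bonferroni-adjusted Wilcoxon signed-rank tests.
4. Repeated-measures ANOVA with Greenhouse-Geisser correction may be added as a stated sensitivity analysis. The correction matters: with unequal correlations between depths the uncorrected test gave 6.2–6.3% type I error, the corrected one 4.7–4.9%.
5. Report the numbers of patients, cores, cuts per depth and complete sets, and label the re-analysis as a change to the plan.
6. If the levels are truly independent groups, say so and keep Kruskal-Wallis with one value per patient.

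The cost is a SAP correction and a re-run on existing section data, with no new samples. Averaging loses between-core detail. Incomplete sets drop out: with 10 complete sets instead of 14, Friedman's power at correlation 0.5 falls from 57% to about 40%. If the correlation is below about 0.2, Friedman's test is somewhat weaker than Kruskal-Wallis.
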